## **Objectives**

*The study has two aims: the primary aim (A1) is to examine differences across the four groups (control, usual care, SM-need, and SM-preference) on caregiver health (health risks and mental and physical health) over time. We hypothesize that the caregivers who receive a self-management intervention based on need (SM-need) or preference (SM-preference) will have better outcomes than those in the usual care or control groups. Secondary aims are to: A2) explore whether caregiver baseline need or preference for intervention (i.e. choice) is associated with: a) care recipient's symptoms; b) caregiver reactions; and c) caregiver involvement and A3) build caregiver profiles from demographic/contextual factors that are associated with their needs and preferences for the self-management interventions (A3).*

*We will also conduct a supplemental analysis to examine relationships among psychological stress responses (caregiver reactions and caregiving involvement), physiological stress responses (heart rate variability domains), and caregiver characteristics (race and gender) in caregivers of people with bipolar disorder. The major aims of the supplemental analysis (SA) are to: SA1) determine whether there are differences by caregiver characteristics (race and gender) on measures of psychological stress responses (caregiving involvement and caregiver reactions), SA2) determine whether there are differences by caregiver characteristics (race and gender) on measures of physiological stress responses (heart rate variability domains), SA3) examine associations among indicators of psychological stress responses (caregiver reactions and caregiving involvement) and physiological stress responses (heart rate variability domains), and SA4) explore relationships among time and frequency domains of heart rate variability.*

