The findings from this study will generate new scientific knowledge about the effectiveness of novel, easy to use, independently performed interventions that can be individualized and self-tailored to promote family caregiver health through education, biofeedback, or resourcefulness. The study will reveal demographic, contextual, and illness-related factors that are associated with caregiver need and preference for self-management intervention(s) to elucidate for whom and under which circumstances an intervention may be most beneficial. This study is clinically significant in testing self-management interventions in a vulnerable, understudied, highly distressed population of caregivers, for whom interventions to promote their own health are critical for their continued service in the caregiving role. Once established, these health self-management interventions can be tailored to match the needs and preferences of other equally distressed family caregivers of persons with other chronic mental or physical conditions.

Bipolar disorder affects men and women equally and rates are not significantly different by race. However, the caregiving experience can differ by gender and race. Female caregivers contribute more time to caregiving and experience greater amounts of role conflict and role strain than male caregivers. Due to caregiving responsibilities, female caregivers are more likely to lose income, lose job benefits, and reduce work hours compared to males.

In studies comparing White and African American caregivers, African Americans generally provide more caregiving hours and perform more caregiver tasks than White caregivers. However, African American caregivers report lower levels of burden and depression than White caregivers. Furthermore, African American caregivers tend to appraise caregiving as less stressful, but are more cognitively impaired and in worse physical health than White caregivers. The supplemental analysis will examine relationships among psychological stress responses, physiological stress responses, and caregiver characteristics in caregivers of people with bipolar disorder. The findings will generate new scientific knowledge about the stress experienced by White and African-American, male and female caregivers of adults with bipolar disorder, using previously untapped measures of heart rate variability to

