Individuals will be assigned a study ID using our enrollment log. In addition, at enrollment we will collect demographic information including age, gender, race, ethnicity, marital status, education, income, occupation, hours of work/week, if the participant is an employee or student at CWRU, health conditions, current medications, relation to person with bipolar, age of family member with bipolar, how many years ago was family member diagnosed with bipolar disorder, specific diagnosis of family member, predominant behavior style of family member with bipolar, whether or not caregiver lives with this family member, whether or not caregiver provides care/assists with basic needs (and how many hrs/day), how many years caregiver has been providing care, if other adults help provide care for family member with bipolar disorder. Some, but not all of the demographic and other questions asked at baseline will also be asked at T2 and T3. We will then proceed with data collection, consisting of surveys to measure bipolar symptoms, caregiver reactions, caregiving involvement, bipolar knowledge, resourcefulness, health risks, and health outcomes. They will also have their heart rate variability (HRV) measured using a non-invasive device on the wrists; it

will take approximately 10 minutes to collect the data. The entire first meeting will take approximately 60-90 minutes. The second and third data collection meeting will be approximately 60 minutes. In the event there is an equipment malfunction or a poor reading is obtained by a research team member, we may need to re-collect the HRV and/or survey data again after a data collection meeting. **COVID-19 modification:** HRV data will not be collected when data collection is done remotely (T2 or T3 only) and will be considered missing data. When we are able to collect HRV data, we will do so by bringing an HRV device to the study participant at a set date and time, providing instructions on how to use the HRV device, safety information on the HRV device, and also providing support via phone or video. HRV data collected this way will be collected for 15-20 minutes instead of 10 minutes, to ensure reliable data is collected. A study team member will collect the HRV device the same day or within 28 hours, at a mutually convenient time. Each HRV device will be sanitized before and after each study participants' use.

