## **Data Analysis Plan**

**Directions: Describe the data analysis plan, including any statistical procedures. If applicable, provide a power analysis, and study/safety endpoints.**

*The primary aim (A1) is to examine differences across four groups of family caregivers on caregiver health over time. The underlying analyses for A1 are built around the repeated measures analysis of variance (RMANOVA). The primary analysis will be a set of 4 group X 3 time waves RMANOVA. These analyses will compare the four groups: 1) a control group (no intervention); 2) education (usual care); 3) SM-need; or 4) SM-preference across three time waves of health risks and physical and mental health outcomes. When using RMANOVA, one not only assesses mean differences across time, but also assesses group differences and the interaction of time X group, which allow us to test the trend of the means over time across the four groups.*

*The RMANOVA, not only can be used to determine if there are mean differences across the three time periods, it can utilize orthogonal polynomial contrasts to determine if there are mean and quadratic trends of the means across time. Orthogonal polynomials are weights assigned to each time period that model a linear or quadratic non-linear trend. RMANOVA can determine if these trends in the mean are significant. A linear trend is indicated if there is a change in direction based on scores across the time waves. The major assumption to be tested with RMANOVA is sphericity. Sphericity is a form of compound symmetry and refers to the equality of variances of the differences between time waves. If the assumption of sphericity is violated based on the Mauchly's test, SPSS provides and adjusted F, df, and P-value in RMANOVA to account for the violation.*

*Secondary aims are to: A2) explore whether caregiver need or their preference for interventions associated with: a) care recipient's symptoms; b) caregiver reactions; and c)*

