caregiving involvement; and **A3**) build caregiver profiles from demographic/contextual factors that are associated with their needs and preferences for the self-management interventions. Accordingly, **A2** will be tested with a series of bivariate analyses including correlations, one way analyses of variance (ANOVA) and independent samples t-tests. We will run correlations when both variables are continuous. If the independent predictor variable is categorical and the dependent outcome is continuous, we will run an ANOVA. When the independent variable is dichotomous and the outcome is continuous, an independent samples t-test will be run. **A3** will build profiles 8 groups from two of the study arms: 1) SM-need and 2) SM-preference. To identify the unique characteristics of each group. Univariate descriptive statistics will be run on the contextual variables within the caregiver, care recipient, and caregiving situation. We will also examine cut points from measures of the self-management processes (knowledge, resourcefulness, and heart rate variability). These analyses will build profiles to show which caregivers may benefit most from a specific self-management intervention. We will prescreen for potential violations of assumptions for correlations. Scatter plots between two variables will identify influential cases, patterns of nonlinearity and constant-error variance that may reduce Parson's  $r$ . To address potential violation of the assumptions, influential cases can be removed. Data transformations can be used to remedy issues such as non-linearity, non-constant error variance, and non-normal error variance. For ANOVAs and t-tests, assumptions of normality and homogeneity of variance will be tested. Non-parametric equivalence tests will be used if assumptions are violated.

For the supplemental analysis, VivoSense software will be used to perform automatic cleaning and computation of heart rate variability measures (SDNN, RMSSD, TP, VLF, LF, HF, LF/HF). Data analysis will consist of descriptive and inferential statistics using SPSS. Description of the sample will include age, gender, race/ethnicity, marital status, education level, annual income, and caregiver relationship. Additionally, descriptive statistics will be calculated for the study measures.

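### Aim A3 describes who needs or prefers each intervention; with no outcome comparison it cannot show who may benefit most, and its need profiles use only one arm's baseline data

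*Combined protocol and SAP*

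**What the plan says.** The Objectives define A3 as an aim to "build caregiver profiles from demographic/contextual factors that are associated with their needs and preferences for the self-management interventions", and the Data Analysis Plan repeats that wording. For the method, the plan says A3 "will build profiles 8 groups from two of the study arms", namely SM-need and SM-preference. It continues: "Univariate descriptive statistics will be run on the contextual variables within the caregiver, care recipient, and caregiving situation". It adds an examination of cut points on knowledge, resourcefulness and heart rate variability (HRV). It then states the purpose: "These analyses will build profiles to show which caregivers may benefit most from a specific self-management intervention".

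The Background has a related phrase. Learning which factors go with need and preference is expected "to elucidate for whom and under which circumstances an intervention may be most beneficial".

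Health outcomes are compared under A1: "The primary analysis will be a set of 4 group X 3 time waves RMANOVA". A2 relates need or preference to the care recipient's symptoms, caregiver reactions and caregiving involvement.

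Study Design/Procedures sets the need category from T1 scores on knowledge, resourcefulness and SDNN (for age and gender). The T1 surveys include "caregiving involvement, bipolar knowledge, resourcefulness, health risks, and health outcomes". HRV is measured at the same meeting, and randomization follows T1.

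**The concern.** Benefit is a difference in outcome against a comparator. To say which caregivers benefit most, that difference must be compared between kinds of caregiver. A3 describes the characteristics of people who fell below a cut score or who picked an intervention. A group can be in clear need, or express a strong preference, and gain nothing from what it receives; the descriptives would look the same either way. If the sentence stands, a report could present profiles of need or choice as evidence of differential benefit that no planned analysis tests.

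A second, smaller matter concerns precision. Taking the eight groups from two arms means the need profiles rest on SM-need alone, although the measures that define need are taken from every caregiver before allocation. This is not bias: under randomized allocation SM-need should resemble the whole sample. If arms are equal, though, about three quarters of the baseline information on need goes unused.

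**Working it through.** **Part 1: is there an outcome comparison by profile anywhere in the plan?**

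| Analysis | Grouping | What is compared | Health outcome? | Comparator by profile? |
|---|---|---|---|---|
| A1 | four whole arms, three waves | health risks, physical and mental health | yes | no |
| A2 | need or preference | care recipient symptoms, caregiver reactions, involvement | no | no |
| A3 | eight need/preference groups | contextual variables; cut points | no | no |
| Supplemental | race and gender, T1 only | stress responses, HRV | no | no |

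No row has both an outcome and a comparator by profile, so nothing stands behind the benefit sentence.

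**Part 2: what using all arms would gain.**

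*The plan's own figure.* Four need categories (education, biofeedback, resourcefulness training, no need) plus four preference categories (the same three, or no intervention) make 8. This reproduces.

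*Availability.* Knowledge, resourcefulness and HRV are collected at T1 with no restriction by arm. Allocation comes afterwards. The COVID-19 gap in HRV is confined to T2 and T3.

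*Inputs.* The total of 360 is from the protocol. The documents give neither an allocation ratio nor category shares. I assume equal arms (360/4 = 90; three arms 270) and shares of 10%, 25% and 40%.

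*Formulas.* The 95% Wilson half-width at a proportion of 0.5 is (1.96/2)/√(n + 1.96²). The half-width for a mean, in SD units, is t(0.975, n−1)/√n.

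| Data used | Share | n in category | 50% characteristic (points) | Mean (SD) |
|---|---|---|---|---|
| SM-need | 10% | 9 | 27.3 | 0.769 |
| SM-need | 25% | 22.5 | 19.1 | 0.438 |
| SM-need | 40% | 36 | 15.5 | 0.338 |
| Three arms | 10% | 27 | 17.6 | 0.396 |
| Three arms | 25% | 67.5 | 11.6 | 0.243 |
| Three arms | 40% | 108 | 9.3 | 0.191 |
| Four arms | 10% | 36 | 15.5 | 0.338 |
| Four arms | 25% | 90 | 10.1 | 0.209 |
| Four arms | 40% | 144 | 8.1 | 0.165 |

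For example, at a 25% share: 0.98/√(22.5 + 3.84) = 0.191 for SM-need, and 0.98/√(90 + 3.84) = 0.101 for four arms.

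*Standard-error ratio against SM-need.* Four arms: √(360/90) = 2.00. Three arms (SM-preference left out): √(270/90) = 1.73. If SM-need holds 80 or 100 caregivers, the four-arm ratio is √(360/80) = 2.12 or √(360/100) = 1.90.

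*Unusable T1 HRV, assumed 5% to 20%.* 360 falls to 342 or 288, and 90 to 85.5 or 72. The sample ratio stays at 4.0.

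**Could a benefit analysis be added instead?** Take SM-need against control within one need category, with 22.5 per arm (equal arms, 25% share, complete follow-up), two-sided 5% and 80% power. The detectable difference is (1.960 + 0.842) × √(2/22.5) = 0.84 SD. A difference in effect between two such categories would have to be about 0.835 × √2 = 1.18 SD.

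**The case against.** The strongest reply is that part 1 is a matter of wording. The descriptives deliver the stated aim, the sentence is hedged with *may*, A3 is secondary, and A1 is unaffected. Most of that is true, and it is why the repair is small. But the hedge supplies no comparison, and the sentence credits these analyses themselves with showing who may benefit. The Background phrase is tied to need and preference, so it is best aligned and not counted as a second error.

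It can also be said that rewording is not the only route: an exploratory need-category-by-arm analysis could be added. That is so, but the detectable differences above make it weak, so rewording is the proportionate choice.

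On part 2, several points stand as limits:
- The plan sets no precision target for A3, so nothing falls short of one, and more T1 data do nothing for the benefit claim.
- The cut scores are introduced as examples, the SDNN thresholds are not given, and no rule covers a caregiver below more than one cut. The rule must be written down before other arms are classified.
- Allocation is by minimization, and the protocol suggests HRV enters its scoring. The factor of 2 is therefore approximate, and the gain may be smaller for characteristics correlated with HRV.
- Poor HRV readings may be re-collected and the monitoring committee reviews missing data, so loss at T1 may be small.

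None of these removes either change.

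**Conclusion.** The concern holds. As planned, A3 can describe which caregivers need or prefer each intervention; it cannot show which benefit. That conclusion needs no numerical assumption. The sentence should be changed, although the primary analysis is untouched.

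The extension to all arms is a cheap improvement to the four need profiles, not the correction of an error. Its size, about half the standard error, rests on equal arms and on treating SM-need as roughly a random quarter of the sample. The interval widths also depend on the assumed category shares. The four preference profiles gain nothing, because the documents describe preference only as a choice made in the SM-preference arm.

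**What to change.** 1. In the Data Analysis Plan, replace the benefit sentence with a statement that the profiles show *which caregivers need or prefer each intervention*, and align the Background phrase. Cost: one sentence and one phrase. If the sponsor wants to keep a benefit question, it needs its own outcome analysis by need category and arm, labelled exploratory and reported with its low power.

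2. Optionally, for precision:
   - Write down the SM-need classification actually used in the trial, including how caregivers below several cuts were assigned.
   - Apply it to the T1 data of all four arms, building need profiles on every caregiver with usable T1 measures. Keep preference profiles in SM-preference.
   - State that SM-preference caregivers (about 90 if arms are equal) then appear in both a need and a preference profile. If disjoint groups are wanted, use control, usual care and SM-need only, which gives three times the SM-need sample instead of four.
   - Report the number with unusable T1 HRV, by arm.

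   Cost: documenting the rule, one rerun of descriptives and one reporting line. No new data are needed and A1 is not affected.

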The aims for the supplemental analysis are to: **SA1**) determine whether there are differences by caregiver characteristics (race and gender) on measures of psychological stress responses (caregiving involvement and caregiver reactions), **SA2**) determine whether there are differences by caregiver characteristics (race and gender) on measures of physiological stress responses (heart rate variability domains), **SA3**) examine associations among indicators of psychological stress responses (caregiver reactions and caregiving involvement) and physiological stress responses (heart rate variability domains, and **SA4**) explore relationships among time and frequency domains of heart rate variability. **SA1** and **SA2** will be tested with a series of independent samples t-tests. **SA3** and **SA4** will be tested with a series of bivariate correlations.

Potential violations of assumptions for correlations and t-test will be assessed. To address violations of the assumptions for correlation, influential cases may be removed. Data transformations may be used to remedy issues such as non-linearity, non-constant error variance, and non-normal error variance. To address violations of the assumptions for t-test, non-parametric equivalence tests will be used if assumptions are violated.

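### Influential cases may be dropped from the correlation analyses with no fixed rule and no all-cases result, so the error rate depends on the analyst's choice

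*Combined protocol and SAP*

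**What the plan says.** Everything on this point is in the Data Analysis Plan section of the combined protocol and SAP.

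- **Where correlations are used.** For A2: "We will run correlations when both variables are continuous". Categorical and two-level predictors go to ANOVA or t-tests. SA3 and SA4 "will be tested with a series of bivariate correlations".
- **How cases are found.** For the main aims: "Scatter plots between two variables will identify influential cases", along with "patterns of nonlinearity and constant-error variance that may reduce" Pearson's r. The supplemental paragraph says only that violations will be checked, not how.
- **What is done then.** Main aims: "To address potential violation of the assumptions, influential cases can be removed". Supplemental analysis: "To address violations of the assumptions for correlation, influential cases may be removed". A second remedy, equally optional, follows in both places; for the main aims it reads "Data transformations can be used to remedy issues such as non-linearity, non-constant error variance, and non-normal error variance".
- **What the other tests get.** For ANOVA and t-tests: "Non-parametric equivalence tests will be used if assumptions are violated". No rank-based counterpart is named for correlations.

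Neither paragraph gives an influence measure, a cut-off, a limit on the number removed, blinding to the result, or a comparison with all cases. No significance level is stated.

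**The concern.** A case is influential because of where it lies relative to the association. Deleting it is therefore a choice that depends on the outcome. Testing Pearson's r on the remaining cases, as if they were the whole sample, ignores that choice. Removing large residuals shrinks the residual variance, so the p-value can be too small. When the choice is made by eye on the plot of the tested pair, the analyst also sees what each deletion does to the result.

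HRV recordings already pass through automatic software cleaning in the supplemental analysis. Cases deleted after that step are likely to be valid caregivers rather than artefacts.

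At stake is whether a reported association between stress reactions and HRV (SA3), or a continuous A2 correlate, can be taken at its stated p-value. Two analysts following the same text could report different answers.

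**Working it through.** **Figure to reproduce.** None. The plan gives no error rate, alpha or power for A2, SA3 or SA4, so the check is a simulation of what the text permits.

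**Inputs from the protocol.** The target sample is 360 (Recruitment Methods), in four groups (Study Design/Procedures). With equal groups, an assumption, one arm is 360/4 = 90 and two arms are 2 × 90 = 180. The n for each correlation is not stated, so 90, 180 and 360 were all used. There are seven HRV measures (Data Analysis Plan).

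**Assumed inputs.** Two-sided 5% level; independent x and y; normal, lognormal, t3 and 5% contaminated normal data; the deletion rules listed below. There were 10,000 replicates at n = 90 and 180, and 5,000 at n = 360.

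**Formulas.** With m cases kept, t = r√((m − 2)/(1 − r²)) on m − 2 degrees of freedom. Cook's distance is D = [e²/(2s²)] × h/(1 − h)², with residual e, residual variance s² and leverage h. The cut-off 4/n is 4/90 = 0.044 or 4/360 = 0.011. The Monte Carlo standard error is √(p(1 − p)/B):

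- √(0.05 × 0.95/10,000) = 0.2 points
- √(0.096 × 0.904/5,000) = 0.4 points
- √(0.25 × 0.75/5,000) = 0.6 points

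**Rejection rate when the true correlation is zero**

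| Analysis | Normal data | Skewed or heavy-tailed data | Share removed (normal, n = 360) |
|---|---|---|---|
| Pearson, all cases | 4.3–5.6% over all settings | | 0 |
| Delete \|z\| > 3 | 4.8–5.2% | 4.6–5.2% | 0.5% |
| Delete Cook's D > 1 | 4.7–5.1% | 2.9–5.4% | 0.0% |
| Delete \|residual\| > 3 | 5.4–5.7% | 4.9–6.8% | 0.3% |
| Delete Cook's D > 4/n | 9.6% at each n | 4.6–9.1% | 5.0% |
| Delete \|residual\| > 2 | 10.9–11.3% | 6.1–11.1% | 4.6% |
| Smaller p of all-cases and Cook's D > 4/n | 8.1–12.1% over all settings | | – |
| Drop one case opposing the trend | 8.2–12.0% over all settings | | 1/360 = 0.3% |
| Drop three cases opposing the trend | 19–31% over all settings | | 3/360 = 0.8% |
| Spearman, all cases | 4.5–5.9% over all settings | | 0 |

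A separate run at n = 90 and 360, with normal, lognormal and t5 data, agrees in pattern:

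- Cook's D > 4/n: about 10% with normal data, 4.2–7.6% otherwise
- |residual| > 3: 4.9–6.1%
- one opposing case dropped: 8.6–12.3%
- Spearman on all cases: 4.2–5.4%

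**Deletion only when an assumption fails.** Cook's D > 4/n was applied only after a Shapiro-Wilk rejection (4,000 replicates). With normal data the trigger fired in about 10% of datasets and the rate was 5.2–6.4%. With lognormal data it always fired, and the rate was 5.6%, 6.6% and 9.1% at n = 90, 180 and 360.

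**Scale for SA3.** Assume one score each for caregiver reactions and caregiving involvement. That gives 2 × 7 = 14 tests. If no association exists, the expected number of false positives is 14 × 0.05 = 0.7 with no deletion, 14 × 0.096 = 1.3 at 9.6%, and 14 × 0.19 = 2.7 to 14 × 0.31 = 4.3 if three opposing cases are dropped each time.

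**Limits of the rank test.** With zero correlation but non-constant error variance, Pearson on all cases rejects in 12–17% and Spearman in 6.3–9.2%. If Spearman is only an option and the smaller p is reported, the rate is 6.1–8.7%.

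**The case against.** The strongest reply is that the plan fixes no rule, so no single inflation figure belongs to it. A reader might infer that removal doubles the false-positive rate. The documents do not support that: it holds for Cook's D > 4/n or |residual| > 2 with near-normal data, but not for strict rules. Removal is also meant for violated assumptions, and normal data are where it is least likely to be triggered. This stands, and it rules out an unconditional headline. It does not rescue the text, because a rule that allows anything from about 3% to 31% does not control the error rate.

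A reader might also infer that the plan tells the analyst to delete only cases that weaken r, since it mentions features that may reduce it. That sentence describes screening and gives no one-sided deletion rule. The 19–31% figure shows what the text fails to prevent, not what it instructs.

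Four further limits stand:

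- **A2.** Intervention need and preference are mainly categorical (education, biofeedback, resourcefulness training or none). They go to ANOVA or t-tests, for which no deletion is planned.
- **SA4.** LF/HF is built from LF and HF, so a zero-correlation null means little for such pairs.
- **SA3 and SA4.** Choosing cases from the scatter plot is stated only for the main aims. For the supplemental analysis it is an inference.
- **Stakes.** Transformation is also a stated remedy, the plan mentions no confidence intervals for these correlations, and the primary aim A1 is untouched.

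**Conclusion.** The concern holds in a limited form. The plan permits open-ended removal of influential cases from its correlation tests and requires no all-cases result. For the main aims it finds those cases with the tested association in view. Depending on the rule used, the false-positive rate stays near 5%, rises to about 10%, or goes well beyond that if several opposing cases are dropped.

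This applies to SA3 and to continuous-by-continuous pairs in A2. In SA4 the worry is a distorted estimate of r rather than type I error. The figures rest on an assumed two-sided 5% level, assumed sample sizes and distributions, and assumed cut-offs. The mechanism does not depend on one particular choice of these, but its size does. As the aims affected are secondary or supplemental, this should be corrected but does not threaten the main comparison.

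**What to change.** Replace the removal sentence in both paragraphs of the Data Analysis Plan with:

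> All cases are retained in the reported analysis. Spearman's rank correlation on all cases is the pre-specified test for these correlations. Pearson's r, transformed-data results and results without influential cases (by a stated influence cut-off) are shown only as sensitivity analyses. A value is excluded only for documented measurement error, judged without reference to the association.

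The influence cut-off for the sensitivity analysis must be written in before the data are examined. Spearman must be the named test, not one of several options, because choosing between it and Pearson after the fact brings back part of the inflation. The change also gives correlations the kind of rank-based approach that the plan already offers as a fallback for ANOVA and t-tests.

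The cost is wording only, with no new data. Spearman is slightly less efficient than Pearson under bivariate normality. It estimates a monotone rather than a linear association and will miss non-monotone ones. It does not fully protect against non-constant variance, and it leaves multiplicity across the series of tests unaddressed.
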